- General demographic and medical history forms
- Medical intake and comprehensive screening assessments performed by clinical research staff at Bellefield Towers or [name] (Oxford Building). Findings will be reviewed for eligibility and signed by a board-certified physician co-investigator ([name]) prior to the infusion. A drug test will also be obtained at intake; urine pregnancy tests may be obtained prior to fMRI scans at the MRRC.

Screening/baseline procedures include pre-infusion psychiatric evaluation, medical screening, and assessment battery (depression/emotional functioning assessments, neuroimaging, cognitive tasks)=1-2 visits over approximately 1-3 weeks

Infusion (ketamine or saline) visit (“Intervention Day 1” in consent form)=one visit, completed within approximately 1 week of baseline assessments

24-hours post-drug assessment battery (“Intervention Day 2” in consent form) (depression/emotional functioning assessments, neuroimaging, cognitive tasks)=one visit completed 24-hours after drug infusion

Cognitive training sessions and brief assessment battery (“Intervention Days 2,3,4,5” in consent form) (depression and suicidality assessments)=eight 15-20min sessions completed 2x/day (sessions separated by >=20 min) on days 1-4 post-infusion

Infusion +5-days assessment battery (“Intervention Day 6” in consent form) (depression/emotional functioning assessments, neuroimaging, cognitive tasks)=one visit completed following completion of all cognitive training sessions

Infusion +7 days remote (questionnaire) assessment (depression assessments)

Infusion +12 days assessment battery (depression/emotional functioning assessments, cognitive tasks)

Infusion +21 days remote (questionnaire/phone) assessment (depression and suicidality assessments)

Infusion +30-days assessment battery (depression/emotional functioning assessments, neuroimaging, cognitive tasks)

Infusion +2, 3, 4, 5, 6 & 12-months remote, naturalistic follow-up assessments (depression/emotional functioning assessments)=questionnaires completed monthly 2-6 months post-infusion and then once more at 12-months follow-up

Total duration of acute study period (after screening is completed)=approximately 4-5 weeks. Includes 1 infusion visit, 5 in-person assessment visits, 2 remote assessments, and 8 brief cognitive training sessions (twice-daily for 4 days post-drug infusion).

Total duration of naturalistic follow-up period=1-year.

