Naturalistic follow-up visits will occur monthly in months 2-6 post-infusion and again at 12 months post-infusion. In addition to other assessments collected during the acute study period, a comprehensive, community treatment questionnaire will be administered to assess the type, dose and duration of medications, psychotherapy, other depression interventions and total inpatient/outpatient visits.

Eligibility Criteria:

Inclusion Criteria:

Participants will:

- 1) be between the ages of 18 and 60 years,

2) have not responded to one or more adequate trials of FDA-approved antidepressants within the current depressive episode, determined by Antidepressant Treatment History Form (ATHF) criteria [score ≥ 1]

3) score ≥ 25 on the Montgomery Asberg Depression Rating Scale (MADRS)(123)

4) score $>1SD$ above the normative mean on the Cognitive Triad Inventory (CTI(127)) “self” subscale(128,129), a well-validated self-report measure of maladaptive self-representations
OR $<1SD$ below the normative mean on the Rosenberg self-esteem scale, a widely used self-report measure of self-esteem

5) possess a level of understanding sufficient to agree to all tests and examinations required by the protocol and must sign an informed consent document

6) agree to sign a release of information (ROI), identifying another individual [friend, family member, etc.] as a contact person while the patient is enrolled in the study.

Exclusion Criteria:

1) Presence of lifetime bipolar, psychotic, or autism spectrum; current problematic substance use (e.g., substance use disorder); or lifetime recreational ketamine or PCP use

2) Use of a Monoamine Oxidase Inhibitor (MAOI) within the previous 2 weeks

3) Failure to meet standard MRI inclusion criteria: those who have cardiac pacemakers, neural pacemakers, cochlear implants, metal braces, or other non-MRI-compatible metal objects in their body, especially in the eye. Dental fillings do not present a problem. Plastic or removable dental appliances do not require exclusion. History of significant injury or surgery to the brain or spinal cord that would impair interpretation of results.

4) Current pregnancy or breastfeeding, or failure to engage in an effective birth control strategy throughout the duration of the study

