****Revised/additional exclusion criterion added on IRB's instruction, effective 08/07/2020 through the end of study****

- 19) Patients with diabetes

Rationale: For the duration of the COVID-19 pandemic, patients with diabetes, who are increased risk of serious complications from COVID-19 exposure, will be excluded.

Statistical Considerations and Statistical Analysis Plan

Sample Size

150 depressed adults will be enrolled in the study and randomized to one of the three treatment arms: ketamine + cognitive training (n=50); ketamine + sham training (n=50); or saline + cognitive training (n=50). Enrollment will continue until a final sample is acquired that includes the full target of n=150 patients who complete, at a minimum, (1) an infusion day, (2) a 24-hour assessment visit, and (3) $\geq 75\%$ of intended Neurocognitive Training (active or sham NT) visits, and will thus be considered to have received their NT allocation.

Power Analyses

Previous studies comparing intravenous ketamine to inert and psychoactive comparators (e.g., midazolam) report large effects at 24-hours ($d=.80$ for depression; $d>3$ for brain activation). The PI's previous mechanistic CT study in depression found large effects ($d=.7-1.0$) on symptom and performance-based cognitive measures. Clinically, we are interested in observation of moderate-large effects. The proposed design will yield 80% power to detect moderate effects based on comparisons of 100 ketamine and 50 saline patients ($d\geq .49$ and $r\geq .31$ using $\alpha=.05$). Based on comparisons of 50 patients in each of the ketamine+CT, ketamine+sham, and saline+CT conditions and 80% power, effects of $d\geq .57$ will be detectable (using $\alpha=.05$). Power for primary mixed effects analyses comparing treatment groups, which increases with additional repeated measures, will be higher than for such post-hoc single-point contrasts.

Analytic Plan

Infusion Phase. Mixed models regression with timepoint (baseline, infusion+24-hours) as a continuous within-subject factor, drug condition (ketamine vs. saline) as a fixed between-subject factor, and subject as a random factor will be applied to test hypothesized time*drug interactions on outcomes. For outcomes where time*drug interactions are observed, direction of effects within each drug condition will be disambiguated using baseline vs. post-infusion contrasts.

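### The within-condition contrasts that follow a time-by-drug interaction are open to regression to the mean; the randomised interaction itself is not

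*Combined protocol and SAP*

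**What the plan says.** The Analytic Plan (Infusion Phase) fits a mixed model to baseline and 24 hours with drug condition between subjects, which "will be applied to test hypothesized time*drug interactions on outcomes". It continues that, only where such an interaction is found, "direction of effects within each drug condition will be disambiguated using baseline vs. post-infusion contrasts". No between-arm contrast at 24 hours is named for stating direction, and regression to the mean is not mentioned.

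Inclusion criterion 3 requires patients to "score ≥ 25 on the Montgomery Asberg Depression Rating Scale (MADRS)(123"). Criterion 4 requires a CTI self score more than 1 SD "above the normative mean on the Cognitive Triad Inventory (CTI(127")), or a score (read here as more than 1 SD) "below the normative mean on the Rosenberg self-esteem scale, a widely used self-report measure of self-esteem".

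The data collection timeline treats screening and baseline together, over one or two visits: "Screening/baseline procedures include pre-infusion psychiatric evaluation, medical screening, and assessment battery". The infusion is "one visit, completed within approximately 1 week of baseline assessments". The documents do not say whether the score that qualified a patient is also the analysis baseline.

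**The concern.** A baseline-to-24-hour contrast inside one arm is an uncontrolled before-after comparison. When patients are admitted because a score was high, a repeat of that score is lower on average even if nothing has happened. The sign of the interaction says how ketamine compares with saline; it does not say which arm moved. The within-arm contrasts are there to settle that, and on the selecting measures they cannot do so reliably.

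Two wrong statements become possible. Inert saline could be reported as having improved patients. Or an interaction produced by worsening on saline could be reported as improvement on ketamine.

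**Working it through.** **1. The plan's own figures.** The Power Analyses section gives 80% power for d of at least .49 (100 vs 50) and .57 (50 vs 50) at alpha .05; sidedness is not stated and two-sided is assumed. The normal approximation is d = (1.960 + 0.842) × √(1/n1 + 1/n2). For 100 vs 50 this is 2.802 × √0.03 = .485; for 50 vs 50 it is 2.802 × √0.04 = .560. With the t distribution the values are .488 and .566. Both stated figures reproduce, and nothing below changes the sample size.

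**2. Inputs for regression to the mean.** From the documents: threshold 25, 100 ketamine and 50 saline patients, two timepoints, and .49 SD as the effect the design can detect. Assumed, because the documents give none of them: the screened pool's mean and SD on the MADRS, the retest correlation ρ, normality, and that the qualifying score is the baseline.

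**3. Expected change with no effect.** With a = (25 − mean)/SD and λ = φ(a)/(1 − Φ(a)), the expected fall is (1 − ρ) × SD × λ. For mean 24 and SD 7, a = 1/7 = .143 and λ = .891. The fall is .1 × 7 × .891 = 0.62 at ρ = .9, 1.25 at ρ = .8 and 1.87 at ρ = .7. It has the same expectation in both randomised arms, so it cancels from their difference.

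**4. What the plan's two-step rule would report.** Simulated trials (20,000 per setting) used a two-sample t-test on change, which with two timepoints and complete data is equivalent to the interaction, and a one-sample t-test on change within each arm. The third and fourth result columns are conditional on a significant interaction; effects are .49 pool SDs (3.43 points when SD is 7).

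| Pool mean, SD, ρ | Fall with no effect | Ketamine works, saline unchanged: saline significantly improved | Saline worsens, ketamine unchanged: ketamine significantly improved | No effect in either arm: significant interaction and significant saline improvement |
|---|---|---|---|---|
| 24, 7, .9 | 0.62 | 29% | 52% | 2.6% |
| 24, 7, .8 | 1.25 | 52% | 83% | 2.4% |
| 24, 7, .7 | 1.87 | 70% | 96% | 2.6% |
| 20, 8, .7 | 2.96 | 94% | 100% | 3.2% |
| 30, 5, .9 | 0.14 | 7% | 9% | 1.8% |

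The last two rows are the extremes over pool means 20 to 30.

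**5. The randomised comparison.** With no effect, the interaction was significant in 4.7% to 5.2% of trials across the settings run, which is the nominal 5% within simulation error. With a true ketamine effect of −3.43 points, the mean between-arm difference was −3.43 to −3.44. The drug-effect test is unbiased and keeps its error rate.

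**The case against.** The strongest reply is that the contrasts are only a second step. They run after a randomised interaction has been observed, and that interaction already carries the direction of the drug effect. This stands. A reader might infer that the ketamine-versus-saline conclusion is biased or that its type I error is inflated; neither follows. A reader might also take the chance of a significant saline contrast in a trial with no effect (about 29% to 71% in the central case if the contrast were always run) as the risk. The plan does not always run it, and the joint event occurs in only about 2% to 3% of trials.

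The scope is also limited, and this too stands. Neuroimaging and cognitive-task outcomes have no stated entry threshold, so they are reached only through correlation with the selecting measures. CTI and Rosenberg are alternatives, so not every patient is selected on either, and CTI is listed among exploratory measures. If baseline is measured separately from the qualifying score, much of the fall precedes it.

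The saline-worsening case is an illustration. The documents describe acute dissociative and euphoric effects of ketamine and an inert comparator, but they give no evidence that blinding failed or that saline patients worsened.

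Simple effects after an interaction are common practice. That does not help here: when a real difference produces the interaction, it does nothing to remove regression to the mean from each arm's own change.

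**Conclusion.** The concern holds for the follow-up rule and not for the interaction test. On the MADRS, and on CTI self or Rosenberg where they are analysed, a within-arm baseline-to-24-hour contrast cannot reliably show what that condition did.

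The size rests on assumptions. Under the central ones it is about 0.6 to 1.9 MADRS points, with an unchanged arm called improved in about 29% to 70% of trials (saline) or 52% to 96% (ketamine) once a true .49 SD difference has produced the interaction. Over pool means 20 to 30 these widen to about 7% to 94% and 9% to 100%. The documents cannot narrow the range. The consequence is misattribution of change to an arm, which calls for a change of wording and no change in design or sample size.

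**What to change.** Replace the sentence on within-condition contrasts with three statements:

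- The direction and size of the drug effect are stated as the ketamine-minus-saline difference at 24 hours with its confidence interval, adjusted for baseline. Name this as the single estimate, so that it does not compete with an unadjusted interaction coefficient.
- Changes within each arm are reported as descriptive means with intervals and are not used to attribute change to either condition.
- One baseline score is defined for all patients. If every patient has a pre-infusion score separate from the qualifying one, use that; otherwise use the qualifying score throughout, so that the definition does not vary between patients.

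The cost is SAP wording, with no new patients or visits. The downside is that the report can no longer claim an effect within one condition. The between-arm difference does not show which arm moved either; the change only stops the report from claiming that it is known.

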Study Protocol

Official Title: Intravenous Ketamine Plus Neurocognitive Training for Depression

ClinicalTrials.gov ID (NCT number): NCT03237286

Initial IRB approval: 08/14/2017

Protocol Date: 08/07/2020; Amended/modified version (study exclusion #19 added)

Scientific Background

Ketamine is a glutamatergic agent used routinely for induction and maintenance of anesthesia. In randomized controlled trials, subanesthetic (typically, 0.5mg/kg) intravenous ketamine exhibits well-replicated, rapid, potent (i.e., metaanalytic Cohen's $d=1.4$, a large effect) antidepressant effects, even in difficult-to-treat conditions such as treatment-resistant depression and bipolar depression. Antidepressant effects begin app. 2 h post-infusion (after acute dissociative and euphoric side effects subside) and continue far beyond the drug's elimination half-life of 2.5-3h. However, effects also dissipate rapidly, with efficacy over placebo fading by 7 days post-infusion. To date, the only strategy shown in replicated datasets to extend ketamine's rapid effects is to give continued ketamine infusions; while some clinicians now offer this service directly to patients, there are substantial feasibility and safety concerns for long-term use, including potential neurocognitive impact and neurotoxicity, dissociative/psychotomimetic side effects, addiction/abuse liability, and burden on patients (e.g., high out-of-pocket expense in community settings) and the healthcare system (e.g., intravenous administration; legal constraints given US schedule III controlled substance status). Alternative administration routes (e.g., intranasal) are under development, but do not circumvent many of these challenges. Attempts to develop alternative pharmaceuticals that either reproduce ketamine's rapid antidepressant effects or extend them after an initial ketamine infusion (e.g., ketamine followed by oral D-cycloserine, which showed promise in a case series of 7 patients) are advancing rapidly, but so far no controlled study demonstrates both rapidity and durability in patients. While these avenues hold tremendous potential, psychiatric care is likely to benefit from a diversity of approaches, including those that efficiently mobilize learning mechanisms to generate gains that are both rapid and enduring.

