Neurocognitive Training Phase. Mixed models regression with timepoint (24-hrs to 30 days) as a continuous within-subject factor, condition (ketamine+NT, ketamine+sham, saline+NT) as a fixed between-subject factor, and subject as a random factor will be applied to test hypothesized treatment and time*treatment interactions on outcomes. Saline+CT will serve as the reference group to test for enduring (main) effects of treatment and for time*treatment interactions.

Exploratory analysis 1 will extend mixed models analysis of depressive symptoms into the 12-month naturalistic follow-up using self-report (primary self-report outcome=QIDS-SR).

Exploratory analysis 2 will utilize a validated data-driven approach to identify integrative/combined moderators of CT effects (DV=MADRS slope), quantified as the optimal weighted combination of moderators (via elastic net w/cross-validation) across all primary + exploratory indices (e.g., fMRI, HNK/BDNF levels, etc.) assessed after ketamine (n=100), defining the data-driven, integrative brain state that optimizes benefit from CT.

Sensitivity analyses will be applied to all hypotheses to explore the impact of main and moderating effects of key biological variables: sex (stratified at randomization to ensure ~60%

female within-cell), age; and baseline clinical variables: treatment-resistance (stratified), concurrent medication.

Exploratory analyses will probe for generalization to other neurocognitive indices and self-report measures [e.g., depressive schemas (CTI); PROMIS measures; QIDS-SR; WHO Disability Assessment Scale].

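### The training-phase model enters time as one continuous term, naturally read as a straight line, which would misstate an early-fading ketamine effect and could label it enduring

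*Combined protocol and SAP*

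**What the plan says.** The Analytic Plan (Neurocognitive Training Phase) specifies mixed models with "timepoint (24-hrs to 30 days) as a continuous within-subject factor", condition as a three-level between-subject factor, and "subject as a random factor will be applied to test hypothesized treatment and time*treatment interactions on outcomes". It adds that "Saline+CT will serve as the reference group to test for enduring (main) effects of treatment and for time*treatment interactions". It gives no time scale (days, log days or visit number), no time origin, no curvature or knot, no categorical alternative and no check of linearity.

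The Scientific Background says of ketamine that "effects also dissipate rapidly, with efficacy over placebo fading by 7 days post-infusion". The Power Analyses section cites d=.80 for depression at 24 hours from earlier studies.

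The data collection timeline has "one visit completed 24-hours after drug infusion", brief depression assessments with the training sessions "on days 1-4 post-infusion", and further depression assessments at days 5, 7, 12, 21 and 30. Counting all of these gives nine acute assessment days, six of them in the first week.

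For the longer term, "Exploratory analysis 1 will extend mixed models analysis of depressive symptoms into the 12-month naturalistic follow-up". That sentence does not restate how time is coded.

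**The concern.** How long the benefit lasts is the trial's central question. If an arm difference changes quickly in the first week and then levels off, one straight line from day 1 to day 30 cannot follow it. The line understates the early difference, carries part of it into later weeks, and spreads the change evenly over the month.

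This reaches a planned output. The plan reads enduring effects from the treatment main effect of this model. In a model with a time-by-treatment term, that coefficient is the fitted difference at whatever day is coded as zero, and the plan does not state that day. A difference confined to the first week can therefore appear as an enduring one.

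**Working it through.** **1. The plan's own figures.** Power = Φ(d/SE − 1.96), with SE = √(1/n₁ + 1/n₂) and two-sided α=.05 (sidedness is not stated).
- 50 vs 50: SE = .20; .57/.20 = 2.85; Φ(.89) = .813.
- 100 vs 50: SE = .173; .49/.173 = 2.83; Φ(.87) = .808.

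Both detectable effects (d≥.57 and d≥.49) reproduce. They concern single time points and do not test the shape of the time course.

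**2. Inputs for the illustration.** From the documents: d=.80 at 24 hours, fading by 7 days, 50 per arm, and days 1, 2, 3, 4, 5, 7, 12, 21, 30. Assumed: raw-day time, the outcome measured at all nine visits, a linear fall to exactly 0 at day 7 and 0 afterwards, no training gain in saline+CT, complete data, equal variances, and within-patient correlation ρ of .4 to .7.

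**3. The fitted line, ketamine+sham minus saline+CT.** With complete balanced data and a random intercept, the model returns the least-squares line through the visit-wise differences.
- True differences: .80, .667, .533, .40, .267, 0, 0, 0, 0. Their sum is 2.667 and their mean .296.
- Mean day = 85/9 = 9.44; Sxx = 1589 − 85²/9 = 786.2.
- Sxy = 6.667 − 85 × 2.667/9 = −18.52; slope = −18.52/786.2 = −.0236 per day.
- Fitted difference at day t = .296 − .0236 × (t − 9.44).

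| Day | True | Fitted |
|---|---|---|
| 1 | .80 | .50 |
| 7 | 0 | .35 |
| 12 | 0 | .24 |
| 21 | 0 | .02 |
| 30 | 0 | −.19 |

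**4. The treatment main effect.** Variance of the fitted difference at day t = (2/50) × [ρ + (1−ρ)/9 + (1−ρ)(t − 9.44)²/786.2].
- Time starting at 24 hours: estimate .50, SE .144 (ρ=.4) to .174 (ρ=.7), z = 3.43 to 2.84, significant in 93% to 81% of trials.
- Time centred: estimate .30, SE .137 to .171, z = 2.17 to 1.73, significant in 58% to 41%.

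The centred figure is the plain average over nine visits, six of them in days 1 to 7. Changing the shape of the time term alone would not alter that average; it also matters which visits define the enduring effect.

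**5. The time-by-treatment test.** At ρ=.5 the slope SE is √(.04 × .5/786.2) = .00504, so z = −.0236/.00504, about −4.7. The model would correctly report a shrinking difference.

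**6. If the trial's hypothesis is right.** Suppose ketamine+CT holds .80 while ketamine+sham fades as above. The true difference between them rises from 0 to .80 by day 7 and stays there. The fitted value is .80 minus the fitted value in step 3: .30 at day 1 (true 0), .45 at day 7 (true .80) and .99 at day 30 (true .80).

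**7. Other choices.**
- Visits on days 1, 5, 12 and 30 only: .50, .37 and .27 at days 1, 7 and 12.
- Nine visits, other fades: the day-7 fitted value is .52 for a step that ends before day 7 (true 0), and .26 to .38 for exponential fades with 5% to 25% left at day 7 (true .04 to .20).
- Log-day time, linear fade, nine visits: .24 at day 7.

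**8. Under the proposed models.** Categorical visits return the step 3 true values in expectation, with SE about .20 per visit. A line with a knot at day 7 also reaches 0 at day 7 and stays there.

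**The case against.** The strongest objection is that the day-7 statement concerns ketamine alone against placebo, and no pair of arms here is that contrast. Saline+CT receives active training, for which the Power Analyses section cites effects of .7 to 1.0. This stands, and it limits the numbers. If saline+CT gains .7 linearly over days 1 to 5 and then holds it, the true difference crosses zero near day 3.6 and the line crosses at day 4.2. With a gain of .35 the days are about 4.6 and 10.8. The line still fits badly: for a gain of .7 it gives .13 at 24 hours against a true .80.

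A reader might infer from the illustration that the trial would report a ketamine advantage lasting to about day 22, followed by a rebound. The documents do not support that. Day 22 is where the fitted point estimate crosses zero in step 3 (9.44 + .296/.0236 ≈ 22.0). The plan outputs no such day, and the figure needs every assumption in step 2. The 95% interval excludes zero only to about day 9.6 (7.8 to 11.7 for ρ of .7 to .3). The day-30 value of −.19 would be significant in only 17% to 18% of trials. With active training in the reference arm, a late advantage for saline+CT could be real.

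Three further points are fair. The protocol says fading by 7 days; it states neither an exact zero nor a plateau. If the arms share the same course, the line creates no treatment effect, so this is misfit under a real early effect and not general inflation of false positives. The Power Analyses section also mentions post-hoc single-point contrasts, which need not come from the line; but the Analytic Plan does not define them for this phase and assigns the enduring effect to the mixed model's main effect.

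**Conclusion.** The point holds as a weakness of specification. The plan names one continuous time term and nothing that would let it bend, against a background statement of rapid early fading and a schedule able to show it. The line misfits under every course tried, whether the difference fades, reverses because training works, or rises and plateaus as hypothesised.

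Under the step 2 assumptions, a difference that is zero from day 7 yields a treatment main effect of about .50 (significant in 81% to 93% of trials) or .30 (41% to 58%), depending on a time origin that the plan leaves open. These sizes are illustrative. The fade to exactly zero, raw-day scale, nine visits, absence of a training gain and ρ are not in the documents. The direction of the time-by-treatment result is not in doubt. This is a low-cost improvement that protects the durability conclusion; it does not invalidate the design.

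**What to change.** - Treat visit as categorical in the training-phase model, with condition-by-visit terms and an appropriate within-patient covariance. Alternatively, use a piecewise-linear model with a pre-stated knot at day 7.
- Define the enduring effect as a contrast at pre-stated later visits of that model, in place of a coefficient whose meaning depends on the time origin.
- Keep the single linear slope as a descriptive summary, and state its time scale and origin.
- State the time coding for exploratory analysis 1. With one raw-day slope over the nine acute days plus days 60, 90, 120, 150, 180 and 365 (assumed), the mean day is 70 and the last visit supplies 295²/142,314 = 61% of Sxx.

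The cost is plan wording and a few degrees of freedom, with some power lost if the true course is linear over 30 days. Because the timeline allows small shifts in assessment days, categorical visits also need stated windows.

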All infusions will be given over 40 minutes and administered in the MUH-CTRC by an experienced team with a linked ACLS-certified code team in a medical hospital setting, with safety/adverse event monitoring sustained for 4-hours post-infusion. Patient safety/decompensation will be monitored at every visit using appropriate exit/referral plans. Patients will be instructed to have nothing by mouth (except for water and coffee) the morning of the infusion and until 2 hours post-infusion.

Randomized, blinded, controlled trials provide the most rigorous method to test intervention effects at any level of analysis. A parallel arm design was selected for primary hypothesis tests due to previously observed cross-over effects in ketamine studies(114) and an anticipated increased risk of unblinding (for both ketamine and CT) if participants can directly compare treatment experiences (e.g., side effects, positive vs. neutral CT stimuli). 2:1 ketamine:saline followed by 2:1 CT:sham randomization was selected to increase probability of benefit to participants(115) and improve recruitment given substantial interest in ketamine from patients and referring clinicians, while maximizing statistical power for key comparisons: ket (n=100) vs. saline (n=50); ket+CT (n=50) vs. ket+sham (n=50) vs. saline+CT (n=50). A 1-month acute follow-up period is feasible and ethical for this initial efficacy study and, if supported, would have a clinically relevant impact, reducing safety and feasibility concerns regarding frequent infusions(28); 12m naturalistic follow-up will further characterize durability and inform frequency for future trials.

Participants will not be withdrawn from existing depression treatments (e.g., medications, therapy). They may continue in existing therapies for the duration of the study, provided they meet all inclusion/exclusion criteria.

Summary of data collection timeline:

The timeline below represents the target day for each set of procedures. At the PI's discretion, the precise day of assessments (e.g., number of days post-infusion) may be adjusted slightly in order to accommodate participant and research facility schedules.

All participants will undergo a medical screening and thorough psychiatric evaluation consisting of a structured diagnostic interview as well as self-report questionnaires to determine eligibility for study participation. Screening assessments for exclusion criteria:

- Initial phone screen

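### The two ketamine arms are treated alike up to 24 hours, but the training-phase model does not use that score as their shared baseline; this costs precision, not validity

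*Combined protocol and SAP*

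**What the plan says.** The Analytic Plan, Neurocognitive Training Phase, specifies one mixed model, whose terms are given as "timepoint (24-hrs to 30 days) as a continuous within-subject factor, condition (ketamine+NT, ketamine+sham, saline+NT) as a fixed between-subject factor". A random effect for each patient is included. The model tests a treatment main effect and a time-by-treatment interaction, with saline+CT as the reference group. It names no covariate and places no constraint on the 24-hour means.

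Study Design & Methods lists among its key comparisons "ket+CT (n=50) vs. ket+sham (n=50) vs. saline+CT (n=50". The Analytic Plan does not write out ketamine+CT versus ketamine+sham as a test.

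The data collection timeline places the "24-hours post-drug assessment battery" on Intervention Day 2, as "one visit completed 24-hours after drug infusion". The eight training sessions run on days 1-4 after infusion, so the first falls on that same day. The Infusion Phase model pools all ketamine patients at 24 hours, and Power Analyses does likewise ("80% power to detect moderate effects based on comparisons of 100 ketamine and 50 saline patients"). Under Sample Size, the target 150 must all have completed that visit ("2) a 24-hour assessment visit").

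**The concern.** For ketamine versus saline, treating the 24-hour score as an outcome is right, because it is measured after the drug. The two ketamine arms differ from each other only in the training that follows. By randomisation their true 24-hour means are equal, so any observed gap is chance. A model that estimates those means freely does two things to this contrast. Its average treatment effect includes a visit where training cannot yet have acted, and it carries the chance gap into that average. It also leaves the main-effect test without the closest available pre-training predictor, each patient's own post-ketamine level. At stake is the chance of detecting a real training effect in the only comparison that holds ketamine constant.

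**Working it through.** **The plan's own figures.** Power Analyses states: "Based on comparisons of 50 patients in each of the ketamine+CT, ketamine+sham, and saline+CT conditions and 80% power, effects of" d≥.57 are detectable. Sidedness is not stated; two-sided .05 reproduces it. With unit SD and 50 per arm, SE = √(2/50) = .20, and the detectable d is (1.96+.84)×.20 = .56. Power at d=.57 is .81. For 100 versus 50, SE = √(1/100+1/50) = .173, the detectable d is .49 and power is .81. Both statements are correct.

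**One later visit, adjusted for the 24-hour score.** SE = .20×√(1−ρ²). For ρ = .3, .5 and .7 (assumed), power at d=.57 is .85, .91 and .98, and the detectable d is .53, .49 and .40.

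**Assumptions for repeated measures (not in the documents).** Depression is measured at days 1, 2, 3, 4, 5, 7, 12, 21 and 30, with 50 per arm. The full effect is d=.40. Correlation is exchangeable at .4 or .6, or decays as .3+.4exp(−Δ/7) or .4+.35exp(−Δ/10), with Δ in days. In the early-plateau shape the effect is 0, .25, .5 and .75 of d at days 1-4 and full from day 5. In the linear shape it grows evenly to day 30. The main effect is read as the equal-weight mean over visits.

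**Worked case, exchangeable ρ=.6, early plateau.**
- Main effect: mean effect (0+.25+.5+.75+5)/9 = .722d = .289. Variance (1+8×.6)/9 = .644, SE √(.04×.644) = .161, power .44.
- Mean of days 5-30, unadjusted: variance (1+4×.6)/5 = .68, SE .165, power .68.
- The same mean adjusted for 24 hours: .68−.6² = .32, SE .113, power .94.
- Chance gap: its SE is .20 SD, so a larger gap occurs in 32% of trials. A .20 SD gap moves the main effect by .20×.644 = .129 SD. At ρ=.4 the shift is .20×(1+8×.4)/9 = .093 SD.

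**Time-by-treatment, same case.** Let x = days since the 24-hour visit: Σx = 76, Σx² = 1428, Sxx = 1428−76²/9 = 786.2.
- Free 24-hour means: slope SE √(.04×.4/786.2) = .00451. The early-plateau slope is .4×(73.5−76×6.5/9)/786.2 = .00947, power .56. The linear slope is .4/29 = .01379, power .86.
- Shared 24-hour mean: information (1/.4)×(1428−(.6/5.8)×76²) = 2076, SE √(.04/2076) = .00439. The early-plateau slope is .4×2.5×(73.5−(.6/5.8)×76×6.5)/2076 = .01079, power .69. Linear power is .88.

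**Range over the correlation patterns, d=.40:**

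| Test of ketamine+CT vs ketamine+sham | As planned or unadjusted | Using the 24-hour score as shared baseline |
|---|---|---|
| Days 5-30 mean, early plateau | 68-79% | 91-94% |
| Time-by-treatment, early plateau | 28-56% | 64-69% |
| Time-by-treatment, linear growth | 48-86% | 63-88% |

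The time-by-treatment rows assume that the fitted model weights visits by their true correlation. With a random intercept alone, the gain under the decaying patterns would be smaller.

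**The case against.** The strongest reply is that the plan also tests time-by-treatment, where the 24-hour score already anchors the slope. This largely stands. A chance gap of +.20 SD moves the fitted 29-day slope difference by only about −.02 to −.09 SD, in the opposite direction. It would therefore be wrong to say that the plan ignores the 24-hour level, or that chance gaps pass for a training effect in every planned test. What remains is a loss of precision, small if benefit grows linearly and correlation is high, larger if benefit comes early and holds.

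A reader might infer bias or an inflated false-positive rate. The documents do not support that: patients are randomised, so the gap averages zero and type I error is 5% overall. Taking visits at 24 hours and days 5, 12 and 30 with ρ .4 to .7, the main-effect test rejects a true null in 24-34% of trials with a .40 SD gap (gaps above that size arise in 5% of trials), but in only 1-4% of those with a .20 SD gap. These departures cancel over all randomisations.

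A reader might also set the planned main effect (44-56% at d=.40, early plateau) against 91-94% and call the difference the cost of this choice. That bundles three changes: dropping the 24-hour visit, dropping days 2-4, and adding the covariate. Dropping only the 24-hour visit gives 52-65%; also adjusting the eight later visits for it gives 83-88%. Replacing the slope test outright could even do harm: under linear growth the adjusted days 5-30 mean has 36-40% power, against 48-86% for the planned slope test.

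Two further points stand. The plan is aimed at moderate to large effects; at d=.70 with an early plateau the main effect already has 88-96% power. And the equal-weight mean is one reading, because with time-by-treatment in the model the treatment coefficient depends on a time coding that is not given.

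**Conclusion.** The point holds as a worthwhile efficiency improvement, not as an error. The documents establish that the 24-hour means are free, that no covariate is named, that the Infusion Phase analysis pools the ketamine arms at 24 hours, and that their comparison is a key one. For that contrast, a .20 SD chance gap shifts the main effect by about .09-.13 SD under the assumed visits and correlations; the interaction is less affected.

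Confidence in the direction of the gain is good: the shared mean raised time-by-treatment power under each shape and correlation tabulated. Its size is less certain, since it rests on an effect shape, visit list and correlations that the documents do not give.

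Two caveats apply. That the 24-hour battery precedes the first training session is implied by the schedule, not stated. And the target sample is defined partly by completing at least 75% of training visits, so within that subset a 24-hour gap could also reflect selection; equality by design belongs to the randomised arms.

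**What to change.** 1. Name ketamine+CT versus ketamine+sham in the Analytic Plan as the contrast that isolates training after ketamine.
2. Keep the three-arm model and the time-by-treatment test, with time counted from the 24-hour visit. Constrain the 24-hour mean to be equal in the two ketamine arms and leave it free in saline+CT. To much the same effect, analyse the visits after 24 hours in the two ketamine arms with the 24-hour score as covariate.
3. Report the arm difference after training ends in addition to time-by-treatment, not in place of it. Estimate it with visits as categories or from the covariate form, so that it does not depend on a straight line.
4. State that the 24-hour battery is done before the first training session.
5. State that contrasts with saline+CT are not adjusted for the 24-hour score, since that would remove part of the ketamine effect.

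The cost is SAP wording and one constraint. No patients or visits are added, and the score should be essentially complete, because the target 150 must attend that visit. The downside is that this contrast is modelled slightly differently from those with saline.
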